6.6. Prior and Concomitant Medication

Prior medications and concomitant medications will be coded using the WHO Drug Dictionary. The number and percentage of participants in the FAS for each prior and concomitant medication will be summarized by WHO drug class and WHO drug PT.

7. EFFICACY

[Appendix A](#) provides a list of data displays. Sample data displays are included in a separate document. The FAS will be used for the analyses of efficacy data.

7.1. Efficacy Hypotheses

Not applicable.

7.2. Analysis of the Primary Efficacy Parameter

[figure not shown]
7.2.1. Objective Response Rate

[figure not shown]
Objective response rate is defined as the percentage of participants experiencing a best overall response of CR/CMR or PR/PMR according to the Lugano criteria ([Cheson et al 2014](#)) for NHL and the iwCLL criteria ([Hallek et al 2018](#)) for CLL

The ORR and its 95% exact binomial CIs will be summarized by cohort. Participants whose baseline disease assessment or on-study response assessments cannot be adequately assessed for response will be considered as nonresponders. These participants will be included in the denominators in the calculations of ORR.

7.3. Analysis of Exploratory Efficacy Variables

8. SAFETY AND TOLERABILITY

[Appendix A](#) provides a list of data displays. Sample data displays are included in a separate document. The FAS will be used for the summary and analyses of all safety data.

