**6. Section 10.2, Populations for Analysis (Table 16: Populations for Analysis)**

**Description of change:** Add a row defining the DLT evaluable set.

**Rationale for change:** This population set will be defined for analyzing DLT results from the dose confirmation part of the study. This population will be more conservative for the calculation of DLT percentage.

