2.2. Study Objectives and Endpoints

[Table 1](#) presents the objectives and endpoints.

Table 1: Objectives and Endpoints

Objectives	Endpoints
Primary	
Dose confirmation period (Phase 1b): To determine the safety, tolerability, and DLTs of combination therapy with tafasitamab + parsaclisib in participants with R/R NHL or CLL who have been previously treated with at least 2 prior lines of systemic antilymphoma therapy.	Incidence and severity of TEAEs and incidence of DLTs.
Dose expansion period (Phase 2a): To assess the preliminary efficacy of combination therapy with tafasitamab + parsaclisib in participants with R/R NHL or CLL who have been previously treated with at least 2 prior lines of systemic antilymphoma therapy.	ORR, defined as the percentage of participants having best response of CR/CMR or PR/PMR per investigator assessment.
Secondary	
To estimate the PK of tafasitamab when given as combination therapy with parsaclisib.	PK parameters of tafasitamab when given in combination with parsaclisib. C_{trough} (ie, predose), C_{max} , t_{max} , C_{min} , and AUC_t will be summarized by descriptive statistics.

Table 1: Objectives and Endpoints (Continued)

Objectives	Endpoints
Exploratory	

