5.3.4. Dose-Limiting Toxicity Evaluable Population

The DLT evaluable population will include participants who have received at least 3 of 4 doses of tafasitamab and 21 days of treatment with parsaclisib 20 mg QD during the first cycle (28 days) or have experienced a DLT. Participants who are considered not evaluable will be replaced.

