8.2.4. Adverse Event Summaries

An overall summary of AEs by cohort will include the following:

- Number (%) of participants who had any TEAEs
- Number (%) of participants who had any serious TEAEs
- Number (%) of participants who had any Grade 3 or higher TEAEs
- Number (%) of participants who had any fatal TEAEs
- Number (%) of participants who had a DLT
- Number (%) of participants who had any TEAEs related to tafasitamab
- Number (%) of participants who had any TEAEs related to parsaclisib
- Number (%) of participants who interrupted tafasitamab because of TEAEs
- Number (%) of participants who interrupted parsaclisib because of TEAEs
- Number (%) of participants who permanently discontinued tafasitamab because of TEAEs
- Number (%) of participants who permanently discontinued parsaclisib because of TEAEs

- Number (%) of participants who had tafasitamab dose reductions because of TEAEs
- Number (%) of participants who had parsaclisib dose reductions because of TEAEs
- Number (%) of participants who withdrew from the study because of TEAEs

The following summaries will be produced by MedDRA term (if 10 or fewer participants appear in a table, a listing may be appropriate):

- Summary of TEAEs by MedDRA SOC and PT
- Summary of TEAEs by MedDRA PT in decreasing order of frequency
- Summary of TEAEs by MedDRA SOC, PT, and maximum severity
- Summary of Grade 3 or higher TEAEs by MedDRA SOC and PT
- Summary of Grade 3 or higher TEAEs by MedDRA PT in decreasing order of frequency
- Summary of serious TEAEs by MedDRA SOC and PT
- Summary of serious TEAEs by MedDRA PT in decreasing order of frequency
- Summary of tafasitamab treatment-related TEAEs by MedDRA SOC and PT
- Summary of parsaclisib treatment-related TEAEs by MedDRA SOC and PT
- Summary of tafasitamab treatment-related TEAEs by MedDRA PT in decreasing order of frequency
- Summary of parsaclisib treatment-related TEAEs by MedDRA PT in decreasing order of frequency
- Summary of tafasitamab treatment-related TEAEs by MedDRA SOC, PT, and maximum severity
- Summary of parsaclisib treatment-related TEAEs by MedDRA SOC, PT, and maximum severity
- Summary of Grade 3 or higher tafasitamab treatment-related TEAEs by MedDRA SOC and PT
- Summary of Grade 3 or higher parsaclisib treatment-related TEAEs by MedDRA SOC and PT
- Summary of tafasitamab treatment-related serious TEAEs by MedDRA SOC and PT
- Summary of parsaclisib treatment-related serious TEAEs by MedDRA SOC and PT

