10.1. Changes to Protocol-Defined Analyses

A DLT evaluable population was added for analyzing results from the dose confirmation part of the study.

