3.2 Adverse Events			
3.2.1	Overall Summary of Treatment-Emergent Adverse Events	FAS	X
3.2.2	Summary of Treatment-Emergent Adverse Events by MedDRA System Organ Class and Preferred Term	FAS	X
3.2.3	Summary of Treatment-Emergent Adverse Events by MedDRA Preferred Term in Decreasing Order of Frequency	FAS	X
3.2.4	Summary of Treatment-Emergent Adverse Events by MedDRA System Organ Class, Preferred Term, and Maximum Severity	FAS	X
3.2.6	Summary of Grade 3 or Higher Treatment-Emergent Adverse Events by MedDRA System Organ Class and Preferred Term	FAS	X
3.2.7	Summary of Grade 3 or Higher Treatment-Emergent Adverse Events by MedDRA Preferred Term in Decreasing Order of Frequency	FAS	X
3.2.8	Summary of Serious Treatment-Emergent Adverse Events by MedDRA System Organ Class and Preferred Term	FAS	X
3.2.9	Summary of Serious Treatment-Emergent Adverse Events by MedDRA Preferred Term in Decreasing Order of Frequency	FAS	X
3.2.10.1	Summary of Tafasitamab Treatment-Related Treatment-Emergent Adverse Events by MedDRA System Organ Class and Preferred Term	FAS	X
3.2.10.2	Summary of Parsaclisib Treatment-Related Treatment-Emergent Adverse Events by MedDRA System Organ Class and Preferred Term	FAS	X
3.2.11.1	Summary of Tafasitamab Treatment-Related Treatment-Emergent Adverse Events by MedDRA Preferred Term in Decreasing Order of Frequency	FAS	X
3.2.11.2	Summary of Parsaclisib Treatment-Related Treatment-Emergent Adverse Events by MedDRA Preferred Term in Decreasing Order of Frequency	FAS	X
3.2.12.1	Summary of Tafasitamab Treatment-Related Treatment-Emergent Adverse Events by MedDRA System Organ Class, Preferred Term, and Maximum Severity	FAS	X
3.2.12.2	Summary of Parsaclisib Treatment-Related Treatment-Emergent Adverse Events by MedDRA System Organ Class, Preferred Term, and Maximum Severity	FAS	X
3.2.14.1	Summary of Grade 3 or Higher Tafasitamab Treatment-Related Treatment-Emergent Adverse Events by MedDRA System Organ Class and Preferred Term	FAS	X
3.2.14.2	Summary of Grade 3 or Higher Parsaclisib Treatment-Related Treatment-Emergent Adverse Events by MedDRA System Organ Class and Preferred Term	FAS	X
3.2.15.1	Summary of Tafasitamab Treatment-Related Serious Treatment-Emergent Adverse Events by MedDRA System Organ Class and Preferred Term	FAS	X
3.2.15.2	Summary of Parsaclisib Treatment-Related Serious Treatment-Emergent Adverse Events by MedDRA System Organ Class and Preferred Term	FAS	X

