3.2.16	Summary of Treatment-Emergent Adverse Events With a Fatal Outcome by MedDRA System Organ Class and Preferred Term	FAS	X
3.2.18	Summary of Treatment-Emergent Adverse Events Leading to Dose Reduction by MedDRA System Organ Class and Preferred Term	FAS	X

Table No.	Title	Population	Standard
3.2.19	Summary of Treatment-Emergent Adverse Events Leading to Dose Interruption by MedDRA System Organ Class and Preferred Term	FAS	X
3.2.20	Summary of Treatment-Emergent Adverse Events Leading to Discontinuation of Study Drugs by MedDRA System Organ Class and Preferred Term	FAS	X
3.2.21.1	Summary of Treatment-Emergent Adverse Events of Tafasitamab Events of Clinical Interest by Events of Clinical Interest Class, Preferred Term, and Maximum Severity	FAS	X
3.2.21.2	Summary of Treatment-Emergent Adverse Events of Parsaclisib Events of Clinical Interest by Events of Clinical Interest Class, Preferred Term, and Maximum Severity	FAS	X
3.2.22	Summary of Dose-Limiting Toxicities	FAS	X

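### The DLT percentage, a Phase 1b primary endpoint, is assigned to the FAS and not to the DLT evaluable population created for it, so the reported rate can be diluted

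*SAP*

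**What the plan says.** SAP Table 1 (Section 2.2) gives the Phase 1b primary endpoint as "Incidence and severity of TEAEs and incidence of DLTs".

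SAP 5.3.4 defines a DLT evaluable population. A participant enters it by receiving the required Cycle 1 exposure to both drugs or by having a DLT; the definition ends "during the first cycle (28 days) or have experienced a DLT. Participants who are considered not evaluable will be replaced". SAP 10.1 gives its purpose: "A DLT evaluable population was added for analyzing results from the dose confirmation part of the study". Protocol Table 16 now carries the same set.

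The analysis text does not use it. SAP 8 says "The FAS will be used for the summary and analyses of all safety data" and makes no exception for DLTs. The overall AE summary in 8.2.4 includes the row "Number (%) of participants who had a DLT". In Appendix A, Table 3.2.1, "Overall Summary of Treatment-Emergent Adverse Events", and Table 3.2.22, "Summary of Dose-Limiting Toxicities", both show FAS in the population column. SAP 8.2.2 provides only a listing of DLTs and names no denominator.

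SAP 5.3.2 puts everyone who received at least one dose of either drug into the FAS. SAP 5.2 calls for a single total per disease cohort, with no split between dose confirmation and expansion.

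**The concern.** The SAP gives the DLT evaluable population a purpose and then sends the result it was meant for to a different population. Followed as written, the primary DLT percentage goes on a denominator that can contain two extra groups:

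- Dosed participants who did not meet the exposure requirement and were replaced. Anyone with a DLT is evaluable, so none of these participants can have had one. They add to the denominator only.
- Up to 10 expansion participants per cohort, because the FAS is not limited to one study period.

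The numerator is also left open. Protocol 6.5.1 defines a DLT through Cycle 1 Day 28 with no limit to one study period, whereas Protocol 10.4.1 lists DLTs for the dose confirmation period. The SAP does not say whether a Cycle 1 DLT in an expansion participant counts in the percentage, so two programmers could report different primary results from the same data.

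What is at stake is the reported tolerability result. It could look more favourable than the rate among the participants on whom the dose was confirmed, and it would not sit on the 10-per-cohort basis used for the precision statements in SAP 3.3.

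**Working it through.** **Plan's own figures.** SAP 3.3 uses n = 10 per cohort throughout.

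- Probability of at least 1 DLT is 1 − (1 − p)^10: 1 − 0.8^10 = 0.893 at p = 20%, and 1 − 0.7^10 = 0.972 at p = 30%. Both match the stated 89.3% and 97.2%.
- One-sided 95% exact upper limit: 25.9% for 0/10, as stated. For 1/10 it is 39.4%, and the stated bound of 39.5% holds.

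So the design figures rest on the 10 evaluable participants, not on the FAS.

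**Inputs.**

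- Evaluable dose-confirmation participants per cohort: 10 (SAP 3).
- Expansion participants e: 0 to 10 (SAP 3); 0, 5 and 10 are shown.
- Dosed participants replaced as not evaluable, r: not given in the documents; assumed 0 to 3. Their DLT count is 0 by the definition in SAP 5.3.4.
- DLTs among the 10 evaluable participants, d: assumed 2, that is 20.0%.

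**Formulas.** FAS size = 10 + e + r.

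- Dose-confirmation DLTs only: reported rate = d/(10 + e + r); ratio to the evaluable rate = 10/(10 + e + r), which cannot exceed 1.
- All Cycle 1 DLTs counted, with expansion participants at the same rate: ratio = (10 + e)/(10 + e + r).

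**Results for d = 2.**

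| Expansion participants, DLTs counted | r = 0 | r = 1 | r = 2 | r = 3 | Ratio, r = 0 to 3 |
|---|---|---|---|---|---|
| e = 0 | 2/10 = 20.0% | 2/11 = 18.2% | 2/12 = 16.7% | 2/13 = 15.4% | 1.00 to 0.77 |
| e = 5, dose confirmation only | 2/15 = 13.3% | 2/16 = 12.5% | 2/17 = 11.8% | 2/18 = 11.1% | 0.67 to 0.56 |
| e = 10, dose confirmation only | 2/20 = 10.0% | 2/21 = 9.5% | 2/22 = 9.1% | 2/23 = 8.7% | 0.50 to 0.43 |
| e = 10, all Cycle 1 DLTs (2 + 2) | 4/20 = 20.0% | 4/21 = 19.0% | 4/22 = 18.2% | 4/23 = 17.4% | 1.00 to 0.87 |

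**Effect on precision.** For 1 DLT, the one-sided 95% upper limit is 39.4% on n = 10, 33.9% on n = 12 and 21.6% on n = 20. An interval computed on the FAS would therefore no longer correspond to the 39.5% statement in SAP 3.3.

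**The case against.** The best counter-argument is that much of the quoted dilution is not specific to the FAS. SAP 5.3.4 does not limit the DLT evaluable population to dose confirmation, so an expansion participant with enough Cycle 1 exposure qualifies too. With 10 such participants that set is also n = 20, and the ratio of 0.50 appears there as well. The part due to the FAS alone comes from replaced participants: 1.00 to 0.77 without expansion, or 1.00 to 0.87 when both periods are pooled in numerator and denominator. This stands, and it is why changing the population name alone would not be enough: the period restriction has to be written in.

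A second argument is that the Protocol ties DLTs to dose confirmation (6.5.3 and 10.4.1), so pairing a dose-confirmation numerator with a two-period denominator is the worst reading. That is fair, but the sentence in 10.4.1 concerns a listing, and the SAP, with one total per cohort on the FAS, does not exclude that reading.

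Third, the Protocol also puts safety on the FAS, Appendix A describes its lists as guidelines, and the table shells are in a separate document. The Protocol repeats the gap and does not close it. Appendix A's latitude stops at changes that affect the nature of an analysis, and the FAS rule is in the body of Section 8 as well. The Amendment 2 rationale for adding the set, "This population will be more conservative for the calculation of DLT percentage", is change-log text and serves only as corroboration; the contradiction is complete within the SAP.

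Lastly, the practical consequence is limited. There is no formal test, and Listing 2.7.6 shows the individual DLTs, so a careful reader could rebuild the count. That bears on severity, not on whether the text is wrong.

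**Conclusion.** The concern holds. SAP 10.1 and SAP 8 with Appendix A cannot both be followed for the DLT percentage. With dose-confirmation DLTs in the numerator, the FAS figure can only equal or understate the rate on the 10 evaluable participants. Under the assumptions shown, the ratio runs from 1.00 (nobody replaced and no expansion) to 0.43 (10 expansion participants and 3 replaced). It runs from 1.00 to 0.87 if expansion Cycle 1 DLTs are counted at the same rate.

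The direction is certain for a dose-confirmation numerator. The size is not, because the documents give no replacement rate and the SAP does not fix the period. The effect is confined to the reported primary result: the iDSMB trigger is a count of participants with DLTs, and the cohort-opening decision uses the first 10 evaluable participants. It should be corrected before the analysis is run, but it does not threaten the conduct of the study.

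**What to change.** - In SAP 8, add an exception to the FAS rule: the DLT count and percentage use the DLT evaluable population restricted to dose-confirmation participants, by cohort.
- In SAP 8.2.4, state that the numerator is DLTs in those same participants.
- In Appendix A, change the population for Table 3.2.22 accordingly. In Table 3.2.1, give the DLT row that denominator with a footnote, or remove the row.
- Optional: keep an FAS version as supportive, add an exact confidence interval on the n = 10 basis of SAP 3.3, and change the listing in 8.2.2 from dose level to cohort, since the study has no dose escalation.

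The cost is SAP wording and two table shells, with no new data. The reported DLT percentage may become less favourable.

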8.1. General Considerations

Summary tables may be replaced with listings when appropriate. For instance, an AE frequency table may be replaced with a listing if it only contains a few unique PTs reported on relatively few participants. Unless otherwise stated, table summaries will be limited to TEAEs.

8.2. Adverse Events

8.2.1. Adverse Event Definitions

A TEAE is any AE either reported for the first time or worsening of a pre-existing event after the first dose of study drug until 90 days after the last dose of study drug. Analysis of AEs (as discussed below) will be limited to TEAEs, but data listings will include all AEs regardless of their timing in relation to study drug administration. For purposes of analysis, all AEs will be considered TEAEs unless the AE can unequivocally be defined as not treatment-emergent.

Adverse events will be tabulated by MedDRA PT and SOC. Severity of AEs will be graded using the National Cancer Institute CTCAE v5.0. The CTCAE reporting guidelines and grading details are available on the Cancer Therapy Evaluation Program website.

The subset of AEs considered by the investigator to be related to study drug will be considered to be treatment-related AEs. If the investigator does not specify the relationship of the AE to study drug, the AE will be considered to be treatment-related. The incidence of AEs and treatment-related AEs will be tabulated. In addition, serious TEAEs will also be tabulated.

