### **6.7.2.2. Live Vaccines**

Because of the immunosuppressive effects of study treatment, administration of any live vaccine is not recommended during the treatment period and at least 6 months after EOT. Thereafter, the decision to administer live vaccines is at the investigator's discretion.

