### **8.3.1. Adverse Events**

Adverse events will be monitored from the time the participant signs the ICF until at least 90 days after the last dose of study treatment or until the start of new anticancer therapy.

Adverse events for enrolled participants that begin or worsen after informed consent should be recorded on the Adverse Events Form in the eCRF regardless of the assumption of a causal relationship with the study treatment. Conditions that were already present at the time of informed consent should be recorded on the Medical History Form in the eCRF. Adverse events (including laboratory abnormalities that constitute AEs) should be described using a diagnosis whenever possible rather than by individual underlying signs and symptoms.

Adverse events will be reported by the participant (or, when appropriate, by a caregiver, surrogate, or the participant's legally authorized representative). The investigator and any qualified designees are responsible for detecting, documenting, and recording events that meet the definition of an AE or SAE and remain responsible for following up on AEs that are serious, are considered related to the study treatment/procedures, or caused the participant to discontinue study treatment. Care will be taken not to introduce bias when detecting AEs and/or SAEs.

Open-ended and nonleading verbal questioning of the participant, such as "How are you feeling?", is the preferred method to inquire about AE occurrences. Adverse events may also be detected when they are volunteered by the participant during the screening process or between visits or through physical examinations, laboratory tests, or other assessments. The definition, reporting, and recording requirements for AEs are described in Section 9.

All SAEs will be reported to the sponsor or designee within 24 hours. The investigator will submit any updated SAE data to the sponsor within 24 hours of it being available.

After the initial AE/SAE report, the investigator is required to proactively follow each participant at subsequent visits/contacts. All SAEs will be followed until resolution, stabilization, the event is otherwise explained, or the participant is lost to follow-up (as defined in Section 7.3).

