## **8.8. Follow-Up**

### **8.8.1. Safety Follow-Up**

The safety follow-up period is the interval between the EOT visit and the scheduled follow-up visit, which should occur 90 days after the EOT visit (or after the last dose of study treatment if the EOT visit was not performed). Adverse events and SAEs must be reported up until 1) at least 90 days after EOT/last dose of study treatment or the start of a new anticancer therapy or 2) until toxicities resolve, return to baseline, or are deemed irreversible, whichever is longer. Reasonable efforts should be made to have the participant return for the follow-up visit and report any AEs that may occur during this period.

If a participant is scheduled to begin a new anticancer therapy before the end of the safety follow-up period, the safety follow-up visit should be performed before a new anticancer therapy is started. Once a new anticancer therapy has been initiated, the participant will move into the survival follow-up period.

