## 9.4. Reporting of Serious Adverse Events

Regardless of suspected causality (eg, relationship to study treatment or study procedures), all SAEs occurring after the participant has signed the ICF through the last safety visit or at least 90 days after the last dose of study treatment *or* until the participant starts a new anticancer therapy must be reported to the sponsor (or designee) immediately, without undue delay but not later than within **24 hours** of obtaining knowledge of its occurrence unless otherwise specified by the Protocol. The investigator will submit any updated SAE data to the sponsor (or designee) immediately, without undue delay but not later than within 24 hours of it being available.

Investigators are not obligated to actively seek SAE information after the safety follow-up visit or 90 days after the last dose of study treatment. If the investigator learns of any SAE, including death, at any time during this period and he/she considers the event to be reasonably related to study treatment or study participation, then the investigator must notify the sponsor (or designee) within 24 hours of becoming aware of the event.

After the initial AE/SAE report, the investigator is required to proactively follow each participant at subsequent visits/contacts. All SAEs will be followed until resolution, stabilization, the event is otherwise explained, or the participant is lost to follow-up (as defined in Section [7.3](#)).

Prompt notification by the investigator to the sponsor regarding an SAE is essential so that legal obligations and ethical responsibilities toward the safety of participants and the safety of a study treatment under clinical investigation are met.

If the SAE is not documented in the RSI of the [parsaclisib IB](#) or the [tafasitamab IB](#) and is thought to be related to the study treatment, the sponsor or its designee may urgently require further information from the investigator for expedited reporting to health authorities. The sponsor or its designee may need to issue an Investigator Notification to inform all investigators involved in any study with the same drug that this SAE has been reported. Suspected unexpected serious adverse reactions will be collected and reported to the competent authorities and relevant ethics committees in accordance with Directive 2001/20/EC or as per national regulatory requirements in participating countries.

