## **9.5. Events of Clinical Interest**

An ECI is an AE (serious or nonserious) that Incyte wishes to document in an organized manner for monitoring or understanding. An ECI does not require rapid communication by an investigator to Incyte unless it meets criteria for rapid communication as an SAE (see Section 9.2).

The following laboratory abnormalities and/or clinical AEs are considered ECIs:

- Tafasitamab:
  - Tumor lysis syndrome
  - IRRs
  - Allergic reactions to study drug  $\geq$  Grade 3
  - CRS
  - Secondary primary malignancy
  - Hepatitis B reactivation
  - Progressive multifocal leukoencephalopathy.

- Parsaclisib:
  - ALT  $\geq 5 \times$  ULN
  - AST  $\geq 5 \times$  ULN
  - Colitis
  - Diarrhea  $\geq$  Grade 3
  - Intestinal perforation
  - Rash  $\geq$  Grade 3
  - Exfoliative dermatitis
  - Pneumonitis
  - PJP infection
  - CMV infection
  - Herpes simplex virus infection
  - Varicella zoster virus infection

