#### **10.4.1. Safety Analyses**

Safety analyses will be conducted for the FAS.

Adverse events will be coded by the MedDRA dictionary, and TEAEs (ie, AEs reported for the first time or worsening of a pre-existing event after first dose of study treatment until 90 days after the last dose of study treatment) will be tabulated by preferred term and system organ class for all events, treatment-related events, events of Grade 3 or higher, serious events, fatal events, and events leading to treatment discontinuation or modification. Dose-limiting toxicities will be listed for participants during the dose confirmation period of the study.

Quantitative safety variables and their changes from baseline (laboratory, vital signs, ECG, etc) will be summarized with descriptive statistics. Abnormal values will be flagged and tabulated based on predefined criteria.

The clinical laboratory data will be analyzed using summary statistics. Descriptive statistics of the value and change from baseline at each assessment time will be provided. For laboratory parameters that have CTC grading, shift tables will be provided showing change in CTC grade from baseline to the worst postbaseline grade. In addition, distributions of key laboratory parameters may be plotted over time; these values will also be classified into NCI CTCAE toxicity grades and tabulated.

Descriptive statistics and mean change from baseline will be determined for vital signs at each assessment time. Vital sign results will be reviewed for clinically notable abnormalities.

Descriptive statistics and mean change from baseline will be determined for each ECG parameter at each assessment time. Electrocardiogram results will be reviewed for clinically notable abnormalities. Participants exhibiting clinically notable ECG abnormalities will be listed.

Measures of exposure (eg, days of exposure, dose intensity, etc) of tafasitamab and parsaclisib will be summarized using summary statistics.

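### TEAEs are counted for 90 days after the last dose in every participant, but AE collection may stop at new anticancer therapy, and the protocol does not say which limit governs

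*SAP*

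**What the plan says.** **What is counted.** SAP Section 8.2.1 defines a TEAE as an AE first reported or worsening "after the first dose of study drug until 90 days after the last dose of study drug". Protocol Section 10.4.1 agrees: "after first dose of study treatment until 90 days after the last dose of study treatment". Neither mentions new anticancer therapy. The SAP adds a default for doubtful cases: "all AEs will be considered TEAEs unless the AE can unequivocally be defined as not treatment-emergent".

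**What is collected.** Protocol Section 8.3.1 monitors AEs "until at least 90 days after the last dose of study treatment or until the start of new anticancer therapy". Section 9.4 joins the same two limits for SAEs with an *or*, and so does the first limb of the reporting rule in Section 8.8.1. None of the three says whether the earlier or the later limit applies.

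**What happens at new therapy.** Section 8.8.1 brings the safety visit forward so that it precedes the new treatment, and then: "Once a new anticancer therapy has been initiated, the participant will move into the survival follow-up period". Section 8.8.3 describes that period as 12-weekly contacts for survival status, with site records supplying later regimens, tumor assessments and OS. In Table 3 the AE row carries nine marks, which fit screening through the safety visit and leave none for disease or survival follow-up.

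**Afterwards.** Section 9.4 states: "Investigators are not obligated to actively seek SAE information after the safety follow-up visit or 90 days" after the last dose. An SAE that the investigator learns of and considers related must still be notified.

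**The concern.** The incidence and severity of TEAEs form part of the Phase 1b primary endpoint (Protocol Table 5). The numerator rests on a window that runs to day 90 after the last dose for every participant, but the data behind it may stop earlier for anyone who starts another treatment.

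Such switching is foreseeable. Treatment continues to progression (Section 4.1), must stop at progression (Section 7.1.1), and may be followed by new antineoplastic therapy as soon as progression is reported (Section 6.7.2.1).

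The consequence depends on how a site reads the *or*. If it stops at new therapy, events inside the counted window go unrecorded. If it records to day 90, events arising on the next regimen enter the database and are counted as TEAEs. Both practices are compatible with the text, so both can occur in one dataset, and AE observation would then differ between sites and participants for reasons unrelated to the combination.

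Elsewhere the sponsor did settle the point. Section 6.7 ends concomitant-medication recording at whichever limit comes first, and Section 10.4.2.1 restricts ORR to responses before new antilymphoma treatment. The AE sections give no equivalent rule.

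**Working it through.** **1. The plan's own safety figures.** The documents give no number for the AE window. The nearest stated figures concern DLTs with 10 participants per cohort, and they reproduce:

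- At least 1 DLT at a 20% rate: 1 − 0.8^10 = 0.8926 (stated 89.3%).
- At least 1 DLT at a 30% rate: 1 − 0.7^10 = 0.9718 (stated 97.2%).
- Exact one-sided 95% upper limit for 0/10: 25.89% (stated 25.9%). For 1/10: 39.42% (stated as not above 39.5%).

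These depend on Cycle 1 only (28 days), so the end of the AE window does not enter them.

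**2. The rules side by side.**

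| Item | Place | End of window |
|---|---|---|
| TEAE, counted | Protocol 10.4.1, SAP 8.2.1 | Last dose + 90 days |
| AEs, collected | Protocol 8.3.1 | At least 90 days *or* new therapy; unresolved |
| AEs/SAEs, reported | Protocol 8.8.1, limb 1 | Same, unresolved |
| SAEs, reported | Protocol 9.4 | Same, unresolved |
| Concomitant medication | Protocol 6.7 | 90 days or new therapy, the earlier |

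The whichever-is-longer phrase in Section 8.8.1 does not settle the matter. It compares limb 1 as a whole with limb 2, the resolution of toxicities, and does not rank 90 days against new therapy inside limb 1.

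**3. Illustration on assumed inputs.** The documents give neither the share starting new therapy within 90 days, nor its timing, nor the event risk after the last dose. Assume a true 90-day risk R = 20% with constant hazard λ = −ln(0.8)/90 per day, and a share f = 50% starting new therapy on day t = 30.

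- Person-time observed if collection stops at new therapy: 0.5 × 30/90 + 0.5 = 67% of the 90 days.
- Collection stops: f(1 − e^(−30λ)) + (1 − f)R = 0.5 × 0.0717 + 0.5 × 0.20 = 13.6%.
- Collection continues and the next regimen adds an equal hazard: f(1 − e^(−(90 + 60)λ)) + (1 − f)R = 0.5 × 0.311 + 0.10 = 25.5%. If it adds twice the hazard: 30.3%.

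Per 20 participants, that is 2.7 or 5.1 (6.1 at twice the hazard) expected with an event, against 4.0 for the combination alone over a full 90 days. Keeping R at 20% and varying f over 25–75%, t over days 14–60 and the added hazard over one to two times gives 7.6% to 18.5% if collection stops and 21.4% to 38.8% if it continues.

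These figures cover only the period after the last dose. The full TEAE window also includes time on treatment, so the effect on total incidence is diluted.

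**The case against.** **The protocol can be read coherently.** The safety visit precedes new therapy and the participant then moves to survival follow-up, so collection of new AEs stops at new therapy while existing toxicities are followed to resolution (Sections 7.1.2 and 8.8.1). This is the most natural reading of Section 8.8.1. But Section 8.3.1 asks for at least 90 days, no section states the rule, and on this reading the TEAE definition still counts time in which no AEs are sought.

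**Temporal is not causal.** Causality is assessed for each drug (Section 9.3), and related TEAEs are tabulated separately for tafasitamab and parsaclisib (SAP Section 8.2.4). This limits misattribution and stands. It does not protect the all-causality tables, and SAP Section 8.2.1 treats an AE with no stated relationship as related.

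**Decisions are little affected.** Expansion rests on DLTs plus ongoing safety review, and there is no comparator and no formal testing. This also stands. The issue is the accuracy of reported TEAE incidence, not the dose-confirmation decision.

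**A stronger reading is tempting.** A reader might set the 90-day window beside the vaccine advice ("administration of any live vaccine is not recommended during the treatment period and at least 6 months after EOT") and the named events of clinical interest, such as "Secondary primary malignancy", and infer that late toxicity is under-counted in the primary endpoint. The documents do not support that. Events after day 90 lie outside the TEAE definition, so not seeking them cannot lower the count. The amendment summary gives a five-half-life rationale for 90 days. Precaution periods are not AE-attribution periods. Related late SAEs remain notifiable, and secondary malignancies are always SAEs (Section 9.2). Actively surveying late events would be a design preference, not a correction.

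**Conclusion.** The mismatch is in the text and should be corrected. Counting runs to 90 days after the last dose for everyone; collection has two limits and no rule for choosing between them; and the participant enters a phase without scheduled AE assessment once new therapy starts. Followed as written, AE observation can be unequal, and next-regimen events can be counted as TEAEs in part of a primary endpoint.

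The size and net direction of the bias cannot be derived from the documents. Under-counting and contamination come from opposite readings, so a reader should not infer that both apply to the same participant or that the net effect has a known sign. The illustrated range shows only that the two readings move the post-treatment proportion in opposite directions; every input to it is assumed. Cycle 1 DLTs are not affected in practice, follow-up of existing toxicities is intact, and the by-drug related tables limit misattribution.

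**What to change.** 1. **Counting.** In SAP Section 8.2.1 and Protocol Section 10.4.1, end the TEAE window at the earlier of 90 days after the last dose and the start of new anticancer therapy. Flag AEs that start after new therapy but within the 90 days, list them separately, and identify those judged related to study drug. The listing will hold what still arrives: related SAEs under Section 9.4 and entries from sites that kept recording.
2. **Collection.** State the same limit for collecting new AEs in Protocol Sections 8.3.1, 8.8.1 (first limb only) and 9.4. Leave unchanged the follow-up of existing toxicities to resolution (Section 7.1.2 and the second limb of 8.8.1) and the notification of related late SAEs (Section 9.4). The earlier-of rule must not replace the whichever-is-longer rule that protects follow-up to resolution.

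**Cost.** Aligned wording in five places, one derived flag and one listing. New antineoplastic therapy is already recorded in the eCRF (Sections 6.7.2.1 and 8.8.3), so no new visit or assessment is needed, and sample size and dosing are untouched. The downside is that TEAE counts may fall slightly, because events starting after new therapy leave the main tables; the separate listing keeps them visible.
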